	
 • Phase III: T-test between Arm A vs Arm B at FU3. • Clinical Response Prediction will be addressed by multiple regression examining relationships between baseline predictor variables (i.e; cognitive profile) and cognitive change scores. • Sample Size and Power This study is powered on the basis of a relative effect size (RES) on Global Cognition of 0.44 at the end of the Phase I RCT (based on average from our Timecourse Trial⁵ and NHMRC SMART trial⁶). Designate power of 0.80 controlling α at 0.05 translates to a required sample size of N=52 (calculated using G*Power 3.1 based on ANOVA repeated measures within-between interaction test, 2 groups, 2 time-points, within subject autocorrelation =0.4, equivalent effect size of [v]=0.22). A sample of N=62 (rounded up from 61) will be recruited to allow for 15% overall attrition (as per Timecourse Trial extrapolated to 9-months).
Duration of the study	3 years

GLOSSARY OF ABBREVIATIONS

ABBREVIATION	TERM
CCT	Computerised Cognitive Training
MCI	Mild Cognitive Impairment
BTS	NHMRC Maintain Your Brain Trial Brain Training System
ADCS-ADL	Alzheimer’s Disease Cooperative Study-Activities of Daily Living
WHOQOL	World Health Organisation Quality of Life
GDS	Geriatric Depression Scale
PSQI	Pittsburgh Sleep Quality Index
APOE 4	Apolipoprotein E 4
BDNF	Brain-derived neurotrophic factor

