3.2 Secondary Objectives

Determine the following:

1. Does the therapeutic cognitive effect differ if training commenced immediately or 3-months later?
2. Does the cognitive state 9-months after entering the trial differ if CCT was commenced immediately or 3-months later?
3. Change in individual cognitive domains measured in separate summary z-score composites
4. Change in daily functional: Amsterdam IADL
5. Change in quality of life: WHOQOL
6. Change in mood and mental-health symptoms: 15-Item GDS
7. Change in sleep-wake patterns: Sleep diary, actigraphy, PSQI
8. Change in risk-perception: Economic Decision Making Competency tool
9. Predictors of cognitive response to CCT: APOE 3/4 and BDNF ValMet polymorphism and baseline cognitive profile.

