The endpoint of FU3 will assess the long-term implication of immediate compared to delayed intervention. If over a 9-month period the timing of a 3-month CCT intervention does not matter, i.e., both arms are cognitively equivalent at the end, then that may influence and inform the distribution of CCT resources in clinics and the community.

Figure 3: Study Hypotheses

Hypotheses

es = effect size

e = endpoint

Primary

Phase I: $es_{A1} > es_{B1}$

Secondary

Phase II: $es_{A1} > es_{B2}$

Phase III: $e_{A3} = e_{B3}$

Assess for eligibility:
Multi-domain MCI criteria
Sleep disturbance criteria
No major neurological/psychiatric/mood disorder

Exclude:
Not meet inclusion criteria
Declined to participate

Written Consent

Enrolment

Baseline Measurements:

- Neuropsychological tests
- Sleep-wake quality
- DNA saliva swab
- Economic decision making

Randomised (n=62)

ARM A
(n=32)

Allocation

ARM B
(n=32)

- Neuropsychological outcomes
- Sleep-wake quality
- Neuroimaging
- Economic decision making
- Review for any adverse events
- Lost to follow-up (reasons)

Follow-up 1
3-months after baseline

- Neuropsychological outcomes
- Sleep-wake quality
- Neuroimaging
- Economic decision making
- Review for any adverse events
- Lost to follow-up (reasons)

- Neuropsychological outcomes
- Sleep-wake quality
- Review for any adverse events
- Lost to follow-up (reasons)

Follow-up 2
6-months after baseline

- Neuropsychological outcomes
- Sleep-wake quality
- Review for any adverse events
- Lost to follow-up (reasons)

- Neuropsychological outcomes
- Sleep-wake quality
- Review for any adverse events
- Lost to follow-up (reasons)

Follow-up 3
9-months after baseline

- Neuropsychological outcomes
- Sleep-wake quality
- Review for any adverse events
- Lost to follow-up (reasons)

- Intention-to-treat analyses: Linear Mixed Model
- Clinical response prediction: Multiple regression
- Excluded from analysis (reasons)

Analysis

- Intention-to-treat analyses: Linear Mixed Model
- Clinical response prediction: Multiple regression
- Excluded from analysis (reasons)

Screening

MCI criteria

MCI is diagnosed according to the Winblad et al 2004 criteria²² confirmed on the basis of consensus rating of multiple clinicians within the memory center.

Typically, this includes a geriatrician or neurologist and two clinical neuropsychologists who review the individual's clinical profile and neuropsychological results.

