10. STATISTICAL METHODS

10.1 Sample Size Estimation

This study is powered on the basis of a relative effect size (RES) on Global Cognition of 0.44 at the end of the Phase I RCT (based on average from our Timecourse Trial⁵ and NHMRC SMART trial⁶). Designate power of 0.80 controlling α at 0.05 translates to a required sample size of N=52 (calculated using G*Power 3.1 based on ANOVA repeated measures within-between interaction test, 2 groups, 2 time-points, within subject autocorrelation =0.4, equivalent effect size of $[\eta^2]=0.22$). A sample of N=62 (rounded up from 61) will be recruited to allow for 15% overall attrition (as per Timecourse Trial extrapolated to 9-months).

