10.3 Statistical Analysis Plan

Phase I: An *intention-to-treat* approach using recommended Linear Mixed Modelling⁴ will evaluate a model including main effects for Group (Arm A vs Arm B), Time (BL vs FU1) and the main interaction term of interest: Group X Time. Covariates will only be added if baseline differences are noted between groups.

Phase II Linear Mixed Modelling⁴ will evaluate a model including main effects for Group (Arm A vs Arm B), Time (Arm A BL vs FU1, Arm B **FU1 vs FU2**) and the main interaction term of interest: Group X Time. An additional covariate of initial global cognitive status will be added to this analysis to control for different potential starting points for the two arms at the different timepoints.

Phase III: Equivalence of the two arms at follow up III will be tested using a two one-sided test (TOST⁴²).

Clinical Response Prediction will be addressed by multiple regression examining relationships between baseline predictor variables (i.e; cognitive profile) and cognitive change scores.

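### Phase III has two incompatible tests, a t-test for difference in the synopsis and a TOST for equivalence in Section 10.3, and the TOST has little chance of success at a margin up to the protocol's nominal effect of 0.44 SD

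*Protocol*

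**What the plan says.** The protocol describes the nine-month comparison in four places.

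- Synopsis, analysis plan: "Phase III: T-test between Arm A vs Arm B at FU3".
- Section 10.3: "Equivalence of the two arms at follow up III will be tested using a two one-sided test".
- Section 4.2: the hypotheses in Figure 3 set the Arm A and Arm B endpoints at the third follow-up equal to each other. The text adds that if "both arms are cognitively equivalent at the end, then that may influence and inform the distribution of CCT resources in clinics and the community".
- Section 3.2, secondary objective 2, asks a difference question: "Does the cognitive state 9-months after entering the trial differ if CCT was commenced immediately or 3-months later". The synopsis objectives do the same.

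Section 10.1 bases the sample size on Phase I alone, with a "relative effect size (RES) on Global Cognition of 0.44 at the end of the Phase I RCT". It continues: "Designate power of 0.80 controlling α at 0.05 translates to a required sample size of N=52". The method is an "ANOVA repeated measures within-between interaction test, 2 groups, 2 time-points" with a within-subject correlation of 0.4. Recruitment of 62 allows for 15% attrition over nine months. The protocol gives no equivalence margin and no power for Phase III.

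**The concern.** The synopsis and Section 10.3 are both current text, and the change table at the front lists only administrative edits. A t-test takes no difference as its null and can only produce evidence that the arms differ. A TOST takes a difference at least as large as the margin as its null and can produce evidence that they do not. With both in the protocol, the choice could be made after the data are seen.

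Section 4.2 attaches a practical use to an equivalence result, namely how training is shared out when not everyone can start at once. In a trial of this size a t-test will often be non-significant when a real difference exists, and next to Section 4.2 that invites the conclusion that timing does not matter. The TOST avoids this error, but the sample was sized for a different question and the TOST may rarely succeed.

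**Working it through.** **Inputs.** From Section 10.1: effect 0.44, power 0.80, α 0.05, correlation 0.4, G*Power effect size 0.22, N = 52 evaluable, 62 recruited, 15% attrition. From Section 4.2: 1:1 allocation. Assumed here: SD 1 (differences in SDs of the composite), a true difference of zero for the TOST, one-sided α 0.05 for each of its two tests, and margins over a range because none is stated.

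**1. The protocol's own figure.** For the interaction test, λ = f² × N × m / (1 − ρ). With f = 0.22, N = 52, m = 2 and ρ = 0.4, λ = 0.0484 × 52 × 2 / 0.6 = 8.39. The noncentral F with 1 and 50 degrees of freedom gives power 0.811; N = 50 gives 0.795. So 52 reproduces, with 0.22 read as Cohen's f. Attrition: 52 / 0.85 = 61.2, hence 62; 62 × 0.85 = 52.7, about 26 per arm at nine months.

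**2. The synopsis t-test.** SE = √(2/26) = 0.277. For a true difference of 0.44 SD the noncentrality is 0.44 / 0.277 = 1.59, against a two-sided critical value of 2.01 on 50 degrees of freedom. Power is about 34%, so about two times in three a difference as large as the nominal effect would be missed.

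**3. The TOST.** Equivalence is concluded when the 90% CI lies inside the margin.

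- Unadjusted half-width: 1.676 × 0.277 = 0.465 SD.
- Baseline-adjusted at r = 0.4: 0.465 × √(1 − 0.16) = 0.426 SD.

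At the expected unadjusted width, even an observed difference of exactly zero fails at a margin of 0.44, because 0.465 exceeds 0.44. Success needs a sample SD that happens to be low. Integrating over the sampling distribution of the SD gives these powers at a margin of 0.44:

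| Setting | Half-width (SD) | Power |
|---|---|---|
| 26 per arm, unadjusted | 0.465 | 2.6% |
| 26 per arm, adjusted, r = 0.4 | 0.426 | 8.2% |
| 31 per arm (no dropout), unadjusted | 0.424 | 8.0% |
| 31 per arm, adjusted, r = 0.4 | 0.389 | 18.1% |
| 26 per arm, adjusted, r = 0.7 (assumed) | 0.332 | 42% |
| 26 per arm, adjusted, r = 0.8 (assumed) | 0.279 | 67% |

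At margins of 0.30 or less, power with 26 per arm is effectively zero at correlations up to 0.4.

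**4. What 80% power would take, unadjusted.** With 26 per arm, a margin of about 0.83 SD. At a margin of 0.44, 90 per arm: 180 evaluable, and 180 / 0.85 = 211.8, so 212 recruited.

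**The case against.** A reader might infer that equivalence cannot be reached at any margin below the assumed effect. The documents do not support that, for four reasons.

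- **No margin is stated.** A margin may properly sit in an SAP that is not shown, so its absence is not a fault. Unadjusted power with 26 per arm is 38% at a margin of 0.60, 60% at 0.70 and about 80% at 0.83.
- **The correlation may be higher than 0.4.** With baseline adjustment, power at 0.44 is 42% at r = 0.7, 67% at 0.8 and about 82% at 0.85. These correlations, and the adjustment itself for Phase III, are assumptions.
- **The benchmark is not firm.** As entered in G*Power, f = 0.22 corresponds to a difference in change of 4 × 0.22 = 0.88 SD, and a margin of 0.83 lies below that. This is a separate question about the Phase I calculation. The effect that the protocol states is 0.44, and the figures here are tied to it.
- **The scale matters.** Section 8 defines the outcome as a weighted average of z-scores, whose SD is below 1 unless the domains correlate perfectly. With its weights (0.40 and four of 0.15), unit-SD domains and an assumed inter-domain correlation of 0.4, the variance is 0.25 + 0.4 × 0.75 = 0.55 and the SD 0.74. A margin of 0.44 raw z-units then gives about 36% unadjusted. The low figures apply to a margin in SDs of the composite.

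It is also fair to say that the synopsis nowhere states that a non-significant t-test will be called equivalence, and that a t-test does address the difference question in Section 3.2. The risk comes from reading the synopsis beside the equality hypothesis and intended use in Section 4.2. Finally, Phase III is secondary, and Section 4.2 says openly that the trial is powered for Phase I.

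These points limit the claim about power. None removes the conflict between the two tests.

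**Conclusion.** The point holds in two parts. First, the protocol names two tests with opposite null hypotheses for one stated hypothesis, and the synopsis test cannot support the conclusion that Section 4.2 hopes to draw. This needs no assumption about margins. Second, the TOST has little chance of success at a margin no larger than 0.44 composite SD: about 3% unadjusted and 8% adjusted at the protocol's correlation, with about 26 per arm, SD 1 and truly identical arms. That is low power under stated inputs, not impossibility.

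The matter should be fixed but does not threaten the trial. The primary Phase I analysis is untouched. Nor do the documents require the equivalence aim to be abandoned: a TOST with a pre-specified margin and an honest statement of its power is a legitimate secondary analysis.

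**What to change.** 1. Remove the Phase III t-test from the synopsis, so that the synopsis, Section 4.2 and Section 10.3 describe one analysis.
2. Report the Arm A minus Arm B difference at the third follow-up, adjusted for the baseline global cognition already collected, with a 90% CI for the TOST and a 95% CI for estimation.
3. Conclude equivalence only if the 90% CI lies wholly inside a pre-specified margin, and state the scale of that margin (composite SDs or raw z-units).
4. State that a non-significant difference, or a CI that merely covers zero, is inconclusive and will not be described as equivalence.
5. State that Phase III is not powered for equivalence at margins up to 0.44 SD under the protocol's own correlation.

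The cost is wording and analysis only, with no added participants, visits or measurements. The downside is that a secondary conclusion becomes less favourable: the likely result is an estimate with a wide interval rather than a finding that timing does not matter.

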2.3 Rationale for Current Study

This RCT will produce three main endpoints:

Firstly, it will determine whether CCT is effective for improving global cognition, thereby providing a potential intervention for the reversal of cognitive decline and prevention of developing dementia for those at high-risk.

The prevalence of MCI is even higher than that of dementia¹⁹. Small gains could have a major impact on prevention of disease burden: a 2-year delay in dementia presentation would for example reduce the prevalence of the disease by 20% by shifting symptom onset (at a population level) beyond natural mortality. With no current effective treatment for dementia and Alzheimer's disease, this endpoint therefore has major significance to human-health, particularly with respect to age-related disease burden.

Secondly, we will learn whether CCT produces secondary gains across a wide variety of important clinical outcomes, including day-to-day function, mood, and quality of life. In particular, assess the impact of CCT on sleep quality in those with sleep disturbance (the first time in MCI). This will also further support the RCT which found CCT improved sleep for participants with disturbed sleep¹⁸ (albeit without MCI). This endpoint will translate to clinically- and personally-relevant information.

Thirdly, this RCT will clarify if the timing of onset of CCT in this clinical population matters. This is of great pragmatic importance, as not all MCI patients can access in-person CCT at the same time.

Fourth, this RCT will examine for the first time in this population if there biological (genetic) or cognitive (profile) predictors of therapeutic response, of great significance for the more selective application of this treatment in MCI and for better resource allocation at a community level.

Accordingly, this endpoint will add fundamental new knowledge highly relevant to clinical practice. Flowing from these endpoints is the expectation of top-quality publications in international peer-reviewed journals, as well data that will directly inform future guidelines for the use of BT in the clinic and in the community. Overall, the outcomes from this project are suggested to be of international medical, scientific and community significance.

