8. CLINICAL AND LABORATORY ASSESSMENTS

Primary Outcome Measure

Global Cognition as defined by pre-specified average of z-scores (referenced to baseline) across following weighted cognitive domains:

1. *Memory (40%)*: Wechsler Adult Intelligence Scale (WAIS) Digit Span²⁴; LOGOS; Wechsler Memory Scale-III Logical Memory I²⁶ and II²⁷, Rey Complex Figure Test-3 minute Recall²⁸.
2. *Speed of processing (15%)*: Trails Making A²⁹.
3. *Language (15%)*: Controlled Oral Word Association Test³¹
4. *Visuospatial skills (15%)*: Rey Complex Figure Test-Copy³¹
5. *Executive functioning (15%)*: Trails Making B²⁹

Secondary Outcome Measures

[figure not shown]
1. Individual cognitive domains measured in separate summary z-score composites
2. Daily functional: Amsterdam IADL
3. Quality of life: WHOQOL
4. Mood and mental-health symptoms: 15-Item GDS
5. Sleep-wake patterns: Sleep diary, actigraphy, PSQI
6. Generalised Axiom of Revealed Preferences (GARP⁴¹)
7. Predictors of responsivity: APOE 3/4 and BDNF ValMet polymorphism, baseline cognitive profile and any other baseline descriptor.

Salival DNA Extraction Swabs Protocol

[figure not shown]
A saliva sample will be collected during baseline measurements to examine APOE4 and BDNF ValMet genotype status. DNA samples will be stored in [name] and analyses will be conducted in [name],

[name] by [name]. BDNF Val/Met polymorphism (rs6265) will be analysed using the Taqman SNP BDNF-AS Assay (SNP ID: rs6265).

[figure not shown]
Oragene•DNA (OG-500)

1. Spit into funnel until the amount of liquid saliva (not bubbles) reaches the fill line shown in picture #1.

[figure not shown]
4. Use the small cap to close the tube tightly.

2. Hold the tube upright with one hand. Close the funnel lid with the other hand (as shown) by firmly pushing the lid until you hear a loud click. The liquid in the lid will be released into the tube to mix with the saliva. Make sure that the lid is closed tightly.

5. Shake the capped tube for 5 seconds. Discard or recycle the funnel.

3. Hold the tube upright. Unscrew the funnel from the tube.

Sleep Actigraphy

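### The response-prediction model regresses change on baseline with no stated arm-by-predictor term, so it cannot show who responds to CCT and tends to favour low baseline scorers even when benefit is uniform

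*Protocol*

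**What the plan says.** Section 3.2 of the protocol lists as its last secondary objective "Predictors of cognitive response to CCT: APOE 3/4 and BDNF ValMet polymorphism and baseline cognitive profile". Section 8 (Secondary Outcome Measures, item 7) names the two genotypes and widens the rest to "baseline cognitive profile and any other baseline descriptor".

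Section 10.3 gives the method: "Clinical Response Prediction will be addressed by multiple regression examining relationships between baseline predictor variables (i.e; cognitive profile) and cognitive change scores". The Synopsis carries the same sentence. Neither place mentions arm, an interaction with arm, the wait-list arm's change, or the interval over which change is taken. In the same section, the Phase I and Phase II models are written out with Group, Time and Group × Time. Section 3.3 likewise plans to relate background variables to change in the outcomes, again without arm.

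Section 2.3 explains the purpose: "predictors of therapeutic response, of great significance for the more selective application of this treatment in MCI".

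**The concern.** A predictor of response to CCT is an effect modifier: a variable along which the difference between trained and untrained participants varies. A regression of change on baseline variables does not estimate that difference. It estimates who changes, for whatever reason.

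For baseline cognition, the one predictor that the analysis sentence names, there is a second problem. The baseline score enters the change score with a minus sign, so the two are negatively correlated unless baseline and follow-up are perfectly correlated. Low scorers will appear to gain more through regression to the mean alone.

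The setting adds further change unrelated to training. Under Screening in Section 4.2, impairment means scoring at least 1.5 SD below estimated premorbid level, and alternate test forms are used only where feasible. Under Section 6.1, most baseline tests come from the clinic assessment. Selection on low scores would push both arms towards apparent improvement; this was not simulated.

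Section 2.3 wants the result to guide selective use of the treatment and allocation of resources. An artefact could be read as grounds for directing training to low scorers.

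**Working it through.** **Inputs.** Section 10.1: "within subject autocorrelation =0.4"; "relative effect size (RES) on Global Cognition of 0.44 at the end of the Phase I RCT"; two-sided 5% level; power 0.80; N=52, raised to 62 for 15% attrition. Synopsis: "equivalent effect size of [v]=0.22". Section 8: "Global Cognition as defined by pre-specified average of z-scores (referenced to baseline) across following weighted cognitive domains", so baseline SD is taken as 1. Allocation is 1:1 (Section 4.2), so 52/2 = 26 completers per arm. Assumed: equal variances at each visit, normality, and the 0.44 read as a constant benefit in baseline SDs for every trained participant.

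**The protocol's own figure.** It gives none for the responder analysis. Its sample size reproduces if 0.22 is treated as Cohen's f: λ = f²·N·m/(1-ρ) = 0.0484 × 52 × 2 / 0.6 = 8.39 on (1, 50) degrees of freedom, power 0.811. N=50 gives 0.795, so 52 is the smallest even N. Attrition: 52/0.85 = 61.2, hence 62. The 0.4 used below is therefore the value on which the plan's N rests.

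**Expected artefact within an arm, uniform benefit.**
- Slope of change on baseline = ρ - 1 = -0.60.
- Variance of change = 2(1-ρ) = 1.2.
- Correlation = -√((1-ρ)/2) = -√0.30 = -0.55; R² = 0.30.
- At ρ = 0.6, 0.8 and 0.9 (assumed): -0.45, -0.32 and -0.22.

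In simulation at ρ = 0.4, trained participants below the baseline median appear to gain about 0.9 SD more than those above it. The true difference is zero.

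**How often it would be declared.** Simulation, 4,000 trials per setting, two-sided 5% test, every trained participant gaining exactly 0.44:

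| Reading of the sentence | n | ρ=0.4 | ρ=0.6 | ρ=0.8 | ρ=0.9 |
|---|---|---|---|---|---|
| (a) Both arms pooled, BL to FU1, predictor is the same composite | 52 | 99% | 91% | 58% | 30% |
| (b) Arm A only, same composite | 26 | 86% | 66% | 36% | 19% |
| (c) Arm A BL to FU1 with Arm B FU1 to FU2, study baseline as predictor | 52 | 51% | 37% | 22% | – |
| (d) As (a), predictor correlating 0.5 with the composite | 52 | 48% | 34% | 18% | – |
| (c) and (d) together | 52 | 16% | 13% | 9% | – |
| With arm, baseline and arm × baseline (BL to FU1) | 52 | 5.0% | 4.4% | 4.8% | 4.7% |

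Repeat runs moved these by a point or two (59% for (a) at ρ = 0.8; 49% for (c) and 50% for (d) at ρ = 0.4). At N=62, reading (a) with ρ = 0.4 gives 99.6%, and the interaction model 5.5%. With no treatment effect at all, reading (a) with ρ = 0.4 still gives 99%, so the artefact does not come from treatment.

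**Check on (c) and (d).** In (c), with equal correlations across visits, Arm B's training change has zero covariance with study baseline, so the pooled correlation is half of -0.548, or -0.274. In (d) it is 0.5 × -0.548 = -0.274 before allowing for the arm difference. By Fisher's transformation, atanh(0.274) × √(52-3) = 0.281 × 7 = 1.97 against 1.96, a rate of about 50%, as simulated.

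**Genotypes.** APOE and BDNF are not components of the change score, so none of these rates applies to them. Their difficulty is only that a model without arm × genotype cannot separate prognosis, or retest gain, from response to CCT.

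**The case against.** The sentence is short. It excludes no arm term, and it names neither interval nor population; an analysis plan not shown here could add an interaction. The study flow chart in Section 4.2 lists multiple regression in the analysis boxes of both arms, so one cannot say that Arm B goes unused. This stands to the extent that the protocol does not rule an interaction out. It does not clear the point. The protocol states the outcome and the predictors, and a model followed as stated does not address the objective. Fitting it separately in each arm would still not compare the arms.

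A reader might infer that a false finding is near-certain. The documents do not support that. The 99% needs ρ = 0.4, which is a planning value, both arms' change measured from study baseline, and a predictor identical to the composite that is differenced. The protocol's predictor is cognitive profile, which may overlap only partly with the composite.

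A reader might also infer that regression to the mean affects APOE and BDNF, or that the predictor list must be cut. The first is wrong, because genotype is not part of the change score. The second does not follow: the evidence here concerns the missing interaction, not the length of the list, and substituting global cognition for cognitive profile would change research question f in Section 2.2.

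Finally, this is the last of nine secondary objectives and leaves the primary Phase I test and its sample size untouched. That bears on priority, not on whether the model is right.

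**Conclusion.** The point holds in this form: the response-prediction model, as stated, cannot identify predictors of response to CCT, and for baseline cognition it is biased towards showing that low scorers respond best. Under a uniform 0.44 SD benefit, equal variances and the protocol's correlation of 0.4, the false-finding rate is about 99% pooled over both arms with the same composite. It is about 86% in Arm A alone, and about 50% if Arm B's change runs from FU1 to FU2 or if the predictor correlates only 0.5 with the composite. At an assumed correlation of 0.8 the pooled rate is about 59%. The lowest rate among the settings examined is 9%, still above the nominal 5%. For APOE and BDNF the defect is confined to the missing arm interaction. The analysis is secondary, so this should be corrected but does not threaten the primary result.

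**What to change.** Replace the sentence in Section 10.3 and the Synopsis with a Phase I model using both randomised arms: FU1 cognition regressed on arm, baseline cognition, the predictor and arm × predictor. Predictors remain baseline cognitive profile, APOE and BDNF; where the predictor is the baseline composite itself, the last term is arm × baseline. Call a variable a predictor of response only on the arm × predictor term, and label the analysis exploratory. With baseline in the model, using change instead of FU1 as the outcome gives the same interaction estimate and test, so the 5% rates above apply.

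This is a wording change on data already planned; no visit, test or participant is added. The cost is precision. At ρ = 0.4 the residual SD is √(1-0.16) = 0.917. For a predictor with SD 1 that explains nothing further, the interaction's standard error with 26 per arm is roughly 0.917 × √(2/26) = 0.25. The 95% interval is then about ±0.50 SD per SD of predictor, wider than the whole planned effect of 0.44. The result will be weaker, but it will answer the question asked.
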